10.4.4. Safety Analyses

All safety analyses will be performed on the Safety population.

AEs will be coded using the latest version of MedDRA available at the start of the study. TEAEs will be summarized for each treatment group by SOC and preferred term (PT), and additionally by severity and relationship to study drug. In addition, the incidence of TEAEs leading to premature discontinuation of study drug and SAEs will be summarized by treatment group, SOC, and PT. Listings of pretreatment AEs, TEAEs, severe TEAEs, AESIs, study drug-related TEAEs, SAEs, TEAEs leading to study discontinuation, and AEs leading to death (if any) will be provided.

Descriptive statistics for observed values and changes from baseline values at each assessment time point will be presented by treatment group for each clinical laboratory, vital signs, and ECG parameters.

The number and percentage of participants with suicidal ideation, suicidal behavior, and self-injurious behavior without suicidal intent will be summarized at each assessment timepoint by treatment group.

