1.3. Schedule of Events and Assessments

Table 1 provides the timing of the events and assessments to be conducted in this study. Also refer to the appropriate sections of this protocol and accompanying study manuals (eg, laboratory, pharmacy, imaging) for more information.

Table 1: Schedule of Events

Period →	Screening	Treatment					Follow-up
Study Day →	Day -60 to -4	Day 1	Day 15	Day 29	Day 58	Day 87/EoT ^a	Day 101
Allowable visit window (days) →			±2	±4	±4	±4	±4
Procedures ↓							
ICF signed	X						
Eligibility evaluation	X	X					
MMSE (see Section 9.2)	X	X ^b				X	
Demography	X						
Medical history	X	X					
Complete physical exam (see Section 9.4)	X						
Symptom-directed physical exam		X	X	X	X	X	X
Weight (W), height (H)	W, H	W	W	W	W	W	W
12-lead ECG ^c	X	X ^b	X	X	X	X	
Vital signs (RR, O ₂ , BP/pulse, including orthostatic) (see Section 9.6)	X	X	X	X	X	X	X
Urinalysis (UTI screening) ^d	X						
Blood sample (genetics; see Section 9.7.1)	X						
Blood sample (chemistry, coag/hematol, lipids)	X	X ^b	X	X	X	X	X
Blood sample (biomarkers)		X ^b	X	X	X	X	X
Blood sample (PK)			X	X	X	predose post: 2,4,6h (±15m) ^e	
C-SSRS (see Section 9.8)	X	All visits (including unscheduled)					
Participant diary (see Section 9.9)	Issued	Each visit: Monitored and filed as source document, new diary issued					Returned
Adverse event monitoring	X	X	X	X	X	X	X

Table 1: Schedule of Events (Continued)

Period →	Screening	Treatment					Follow-up
Study Day →	Day -60 to -4	Day 1	Day 15	Day 29	Day 58	Day 87/EoT ^a	Day 101
Allowable visit window (days) →			±2	±4	±4	±4	±4
Procedures ↓							
Prior & concomitant meds (see Sec. 8.7)	X	X	X	X	X	X	X
Cognitive battery (see Section 9.11)	X ^f	X ^b	X	X	X	X	X
EEG, ERP (see Section 9.12)	X	X ^b	predose, and at 2h (±30m) postdose				X
Neuroimaging (rs ASL, fMRI) (see Sec. 9.13)	X ^g	X ^b	4 (±1½) h post			4 (±1½) h post	
CSF sampling (biomarkers & PK)	X ^h					6h (±15m) post ^e	
Study drug dosing ⁱ , supply, accountability		X	X	X	X	X	

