12. Suicidality, defined as active suicidal thoughts during the 6 months prior to Screening visit or at Day 1 (eg, Type 4 or 5 on the Columbia-Suicide Severity Rating Scale [C-SSRS]), or history of suicide attempt in previous 2 years, or at serious suicide risk, in investigator's judgment
13. Resides in a nursing home or assisted care facility with need for continuous direct medical care and nursing supervision. *Exception:* Participant may reside in such facility provided that continuous direct medical care is not required, a qualified caregiver is available for co-participation, and the participant is physically able to attend in-clinic study visits.
14. Family history of short QT syndrome or long QT syndrome
15. Clinically significant cardiac involvement or an ECG with corrected QT interval using Fridericia's formula (QTcF interval) >450 ms for men or >470 ms for women.
Note: If the first ECG QTcF interval obtained is out of range, the ECG should be repeated twice and the average of the 3 results should be used to determine eligibility.
16. Any surgery or hospitalization in the 4 weeks prior to enrollment (*Exception:* minor dermatologic procedures)
17. Recent history (eg, within prior 2 years) of 1 or more CNS bleeding event requiring intervention and/or hospitalization

18. Any of the following at Screening or predose on Day 1:

- Alanine transaminase $>2.0 \times$ upper limit of normal (ULN) as defined by laboratory
- Aspartate transaminase $>2.0 \times$ ULN as defined by laboratory
- Total bilirubin $>1.5 \times$ ULN as defined by laboratory (isolated bilirubin $>1.5 \times$ ULN is acceptable if total bilirubin is fractionated and direct bilirubin $<35\%$)
- Current or recent (within prior 12 months) hepatic disease

19. Current use of aspirin ≥ 325 mg/day, any P2Y12 inhibitor, any anticoagulant medication, specific inhibitors of phosphodiesterase 5 (PDE5), nonspecific inhibitors of PDE5 (including dipyridamole and theophylline), any supplement for the treatment of erectile dysfunction, riociguat, vericiguat, any nitrate.

[REDACTED] medications are prohibited from the Screening visit through the duration of the study. See [Appendix 3](#).

20. History or presence of severe gastrointestinal dysmotility (eg, dyspepsia, stomach aches, nausea, vomiting, recurrent pancreatitis, constipation) as determined by the investigator that may impact compliance and/or oral drug administration, absorption, and exposure

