9. STUDY ASSESSMENTS AND PROCEDURES

Study assessments will be conducted according to the timing and sequence indicated in the [Schedule of Events](#). Details regarding those procedures are provided below and in the study manuals (eg, laboratory, pharmacy, imaging).

During any unscheduled visit, safety assessments will be conducted per investigator discretion; results will be documented in the source document and the appropriate eCRF.

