10.4.1. General Considerations

Continuous variables will be summarized using the number of participants, mean, SD, minimum, median, interquartile range, and maximum values. Categorical variables will be summarized using the frequency and percentage of participants in each category. Percentages will be based on the total number of participants with non-missing values. If there are missing values, the number missing will also be presented, but without a percentage. Data summaries will be presented by treatment group (placebo, CY6463). All available data will be included.

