10.4.2. Primary Endpoint(s)

Corresponding with the primary objective of evaluating the safety and tolerability of CY6463, TEAE incidence (number and percentage of participants with TEAEs) will be reported for each

treatment group for the Safety population. A TEAE is defined as an AE that started on or after the administration of randomized study drug through the last day of the Follow-up period.

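### The C-SSRS is summarized timepoint by timepoint only: no by-arm count of participants with new or worsened post-dose findings, and no rule for placing unscheduled ratings

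*Combined protocol and SAP*

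**What the plan says.** **Collection.** Table 1 (Section 1.3) has the C-SSRS at Screening and then at "All visits (including unscheduled"). Section 9 states a more general rule: "During any unscheduled visit, safety assessments will be conducted per investigator discretion".

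**Analysis.** Section 10.4.4 reports counts and percentages for three C-SSRS categories. Ideation and behavior are the first two, and the sentence ends with this: "self-injurious behavior without suicidal intent will be summarized at each assessment timepoint by treatment group". That is the only C-SSRS summary. The same section does compare with baseline for other safety data ("Descriptive statistics for observed values and changes from baseline values at each assessment time point will be presented by treatment group"), but only for laboratory, vital sign and ECG parameters. The baseline definition in Section 10.4.3 is written for the exploratory endpoints. Section 10.4.1 adds "All available data will be included".

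**Related outputs.** Section 10.4.4 also states "TEAEs will be summarized for each treatment group by SOC and preferred term (PT"), and Section 10.4.2 fixes the onset window: "A TEAE is defined as an AE that started on or after the administration of randomized study drug through the last day of the Follow-up". Appendix 2 makes suicidality TEAEs an adverse event of special interest (AESI). Section 10.4.4 lists AESIs but plans no by-arm AESI table.

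**Entry.** Exclusion 12 (Section 7.2) covers "active suicidal thoughts during the 6 months prior to Screening visit or at Day 1", with Type 4 or 5 ideation given as an example.

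**The concern.** Safety is the primary objective. Section 9.8 describes the drug as CNS-active and gives that as context for monitoring suicidality. For such a scale a safety reader wants to know how many participants in each arm had a finding after the first dose that they did not have, or had in milder form, before it. A series of by-visit percentages does not answer that. It does not show whether the participant counted at one visit is the one counted at the next, or whether that participant was already positive at Screening or Day 1.

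Unscheduled ratings are the second difficulty. A rating taken between visits may well be prompted by a concern about the participant, yet nothing says which row of the summary it enters. The sponsor's Data Review Committee sees unblinded data only in aggregate (Section 6.3.2), so it depends on what the by-arm tables can show.

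**Working it through.** The plan gives no C-SSRS rate, and its sample size is stated to be non-statistical (Section 10.2), so there is no figure to reproduce. The arithmetic below only shows what the planned table can and cannot distinguish. Post-dose means after the first dose of study drug.

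**Inputs**
- About 30 randomized (Sections 6.2 and 10.2) at 1:1 (Section 6.3.1): 30 / 2 = 15 per arm. I assume all are dosed and rated at every visit.
- Scheduled pre-dose ratings: Screening and Day 1. Under the note to Table 1, assessments on dosing days precede the dose unless otherwise stated.
- Scheduled post-dose ratings: Days 15, 29, 58, 87 and 101, which is 5.

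**Step 1. Weight of one participant.** 1/15 = 6.7% of an arm.

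**Step 2. Distinct participants behind the by-visit rows.** If the rows show counts c1 to c5, the number of distinct participants D satisfies max(c) ≤ D ≤ sum(c), capped at 15. With 1/15 in every row, max = 1 and sum = 5, so D lies between 1/15 = 6.7% and 5/15 = 33.3%.

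**Step 3. Do the pre-dose rows settle it?**
- If Screening and Day 1 both show 0/15, every later case is new, but D can still be anything from 1 to 5.
- If both show 1/15, the same seven rows arise when one participant is positive throughout (0 new cases) and when that participant resolves and five others are each positive once (5 new cases, 33.3%).
- Ideation is counted as present or absent, so a rise from a lower to a higher ideation type in the same participant changes nothing in the table.

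**Step 4. Unscheduled ratings.** One participant positive only at an unscheduled visit is 6.7% of an arm, with no stated row.

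**Step 5. Precision of the missing count.** The exact (Clopper-Pearson) 95% limits are the 0.025 quantile of Beta(x, n−x+1) and the 0.975 quantile of Beta(x+1, n−x), with n = 15:

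| Participants new or worsened | Percent | Exact 95% interval |
|---|---|---|
| 0 | 0.0 | 0 to 21.8 |
| 1 | 6.7 | 0.2 to 31.9 |
| 5 | 33.3 | 11.8 to 61.6 |

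**Step 6. What the adverse event route covers.** A C-SSRS finding reaches the TEAE table only if it is recorded as an adverse event. Under Appendix 2 an abnormal safety assessment qualifies when the investigator judges it clinically significant. Section 9.8 asks for a risk assessment after a positive Item 4, Item 5 or behavioral answer, and does not instruct that an adverse event be recorded. For ideation below Item 4 it sets no specific trigger. For findings not recorded as adverse events, the by-timepoint table is the only by-arm summary.

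**The case against.** The strongest reply is that suicidality is already handled through adverse events. A reader might infer from the C-SSRS paragraph that new on-treatment suicidality is not counted by arm at all. The documents do not support that. TEAEs are tabulated by arm, must start on or after the first dose, and do not depend on a scheduled visit. Appendix 2 also treats worsening of a pre-existing condition, and clinically significant worsening of a safety assessment, as adverse events. This part of the reply stands and limits the point to findings not recorded as adverse events.

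Three other strong readings also fail:
- *Unscheduled ratings are excluded.* The text is silent rather than exclusive. Section 10.4.4 does not restrict the table to scheduled visits, whereas Section 10.4.3 does so for PK concentrations, and Section 10.4.1 includes all available data. What is missing is a placement rule.
- *Carried-over ideation would pass for a drug or placebo effect.* Screening and Day 1 are timepoints in the same table, so pre-dose prevalence is visible by arm. Only the link within a participant is lost.
- *Exclusion 12 admits everyone with lower-grade ideation.* Type 4 or 5 is only an example. The criterion also excludes a suicide attempt in the previous 2 years and anyone the investigator judges at serious risk. Lower-grade ideation is not clearly excluded, but how many such participants would enroll is unknown.

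Finally, Section 10.4 defers technical detail to a SAP, and a shift table or visit-mapping rule could sit there. No separate SAP text is in the material available, so this cannot be confirmed. If the SAP already contains them, the analysis part of the point is met.

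**Conclusion.** The point holds in a limited form. As written, Section 10.4.4 provides no by-arm count of distinct participants with C-SSRS findings that are new or worse than before dosing, and no rule for placing the unscheduled ratings that Table 1 requires. The gap concerns findings not recorded as adverse events and the missing within-participant comparison. It does not mean that suicidality goes uncounted.

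Its size, on the assumption of 15 fully rated participants per arm, is that 1/15 at all five scheduled post-dose visits is compatible with anything from no new case to five new cases (0 to 33.3%), with the pre-dose rows unable to separate these extremes when they also show 1/15. This is an illustration of ambiguity, not a forecast, because the documents give no expected rate of ideation. The analysis is descriptive and the trial small, so this is an inexpensive improvement worth making. It does not invalidate the safety analysis.

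**What to change.** Keep the by-visit table and add to Section 10.4.4, by arm on the Safety population:

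- **(a)** the number and percentage of participants with any post-dose suicidal ideation, any post-dose suicidal behavior, and any post-dose self-injurious behavior without suicidal intent, using all scheduled and unscheduled ratings;
- **(b)** a shift table from the worst pre-dose category (Screening and Day 1) to the worst post-dose category, giving the number new or worsened.

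State in the same place how unscheduled ratings are treated in the by-visit table, for example that they enter (a) and (b) but no visit row.

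Separately, Section 9 leaves safety assessments at unscheduled visits to the investigator's discretion, while the Table 1 C-SSRS row includes those visits. The two must be reconciled, since the completeness of the unscheduled ratings depends on which applies.

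The cost is one additional table from data already collected, plus a few sentences of text.

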10.4.5. Other Analyses

Potential relationships between CY6463 plasma concentrations and PD exploratory assessments may be assessed.

10.5. Interim Analyses

No formal interim analysis is planned for this study. Study data will be reviewed by an unblinded DRC as specified in Section [6.3.2](#).

APPENDIX 1. REGULATORY, ETHICAL, AND STUDY OVERSIGHT CONSIDERATIONS

Direct Access to Source Data/Documents

Study Monitoring

Before an investigational site can enter a participant into the study, a representative of the sponsor will visit (in person or remotely, as necessary) the investigational study site to:

- Determine the adequacy of the facilities
- Discuss with the investigator(s) and other personnel their responsibilities with regard to protocol adherence, and the responsibilities of the sponsor or its representatives. This will be documented in a clinical study agreement between the sponsor and the investigator.

During the study, a monitor from the sponsor or its representative will have regular contact with each study center for the following purposes:

- Provide information and support to the investigator(s)
- Confirm that facilities remain acceptable
- Confirm that the study team is adhering to the protocol, that data are being accurately recorded in the eCRFs, and that study drug accountability checks are being performed
- Perform source data verification. This includes a comparison of the data in the eCRFs with the participant's medical records at the hospital or practice, and other records relevant to the study. This will require direct access to all original records for each participant (eg, clinic charts).
- Record and report any protocol deviations not previously sent to the sponsor
- Confirm AEs and SAEs have been properly documented on CRFs and confirm any SAEs have been forwarded to the sponsor and that those SAEs that met criteria for regulating reporting have been forwarded to the IRB.

The monitor will be available between visits if the investigator(s) or other staff needs information or advice.

Audits and Inspections

Authorized representatives of the sponsor, a regulatory authority, an IEC or an IRB may visit the site to perform audits or inspections, including source data verification. The purpose of an audit or inspection is to systematically and independently examine all study-related activities and documents to determine whether these activities were conducted, and data were recorded, analyzed, and accurately reported according to the protocol, good clinical practice (GCP) guidelines of the ICH, and any applicable regulatory requirements. The investigator should contact the sponsor immediately if contacted by a regulatory agency about an inspection.

Institutional Review Board (IRB)/Independent Ethics Committee (IEC)

The principal investigator at each study centers must obtain IRB/IEC approval for the study. Initial IRB/IEC approval and all materials approved by the IRB/IEC for this study, including participant ICF(s) and recruitment materials, must be maintained by the investigator and made available for inspection.

Quality Control and Quality Assurance

To ensure compliance with GCP and all applicable regulatory requirements, the sponsor may conduct a quality assurance audit. See [Audits and Inspections](#), above.

Ethics

Ethics Review

The final study protocol, including the final version of the ICF(s), must be approved or given a favorable opinion in writing by the respective study center's IRB/IEC. The investigator must submit written IRB/IEC approval to the sponsor/sponsor's designee before enrolling a participant into the study.

The principal investigator of the respective study center is responsible for informing the IRB/IEC of any amendment to the protocol in accordance with local requirements. In addition, the IRB/IEC must approve all participant-facing materials, including but not limited to advertising used to recruit participants for the study. The protocol must be re-approved by the IRB/IEC upon receipt of amendments and annually, as local regulations require.

The principal investigator of a respective study center is also responsible for providing the IRB/IEC with reports of any reportable serious adverse drug reactions from any other study conducted with the study drug. The sponsor/sponsor's designee will provide this information to the principal investigator.

Progress reports and notifications of serious adverse drug reactions will be provided to the IRB/IEC according to local regulations and guidelines.

Ethical Study Conduct

The study will be performed in accordance with ethical principles that have their origin in the Declaration of Helsinki and are consistent with ICH/GCP, applicable regulatory requirements and sponsor policy.

Informed Consent

The principal investigator(s) at each study center will ensure that each participant (and/or LAR and the participant's caregiver/study partner, as applicable [see [Eligibility Inclusion 1](#)]) is given full and adequate oral and written information about the nature, purpose, possible risk and benefit of study participation. A participant will not undergo any study procedure unless and until both the participant (and/or the participant's LAR, if applicable) sign the ICF(s). The ICF(s) will be written in such a way that at minimum, the LAR and caregiver/study partner, as applicable, understand the implications of study participation. The participant (and

LAR/caregiver/study partner, as applicable) will be given the opportunity to ask questions and allowed time to consider the information provided. Participants must also be notified that they are free to discontinue from the study at any time.

The principal investigator(s) must maintain the original, signed ICF(s). A copy of the signed ICF(s) must be given to the participant (and to the LAR/caregiver/study partner, as applicable).

Participants who are rescreened are required to sign a new ICF.

Data Handling and Recordkeeping

Data Protection

- Participants will be assigned a unique identifier by the sponsor. Any participant records or datasets that are transferred to the sponsor will contain the identifier only; participant names or any information that would make the participant identifiable will not be transferred.
- The participant must be informed that his/her personal study-related data will be used by the sponsor in accordance with local data protection law. The level of disclosure must also be explained to the participant who will be required to give consent for their data to be used as described in the ICF.
- The participant must be informed that his/her medical records may be examined by the sponsor's quality assurance auditors or other authorized personnel appointed by the sponsor, by appropriate IRB/IEC members, and by inspectors from regulatory authorities.

Inspection of Records

The sponsor or sponsor's designee will be allowed to conduct site visits to the investigation facilities for the purpose of monitoring any aspect of the study. The investigator agrees to allow the monitor to inspect the drug storage area, study drug stocks, drug accountability records, participant charts and study source documents, and other records relative to study conduct.

Retention of Records

Principal investigators must maintain all documentation relating to the conduct of this study for a period of 2 years after the last marketing application approval of CY6463 or, if not approved, 2 years after discontinuance of its development. If it becomes necessary for the sponsor or a regulatory authority to review documentation relating to the study, the investigator will permit access to such records.

Publication Policy

All data generated in this study will be the property of the sponsor. An integrated clinical and statistical report will be prepared at the completion of the study.

Please refer to the study center clinical trial agreement for publication and disclosure information.

APPENDIX 2. ADVERSE EVENTS, AESIS, AND SAES: DEFINITIONS AND PROCEDURES FOR RECORDING AND EVALUATING

Definition of Terms

Adverse Event (AE)

Per ICH, AEs are defined as any untoward medical occurrence in a patient or clinical study participant administered a pharmaceutical product and which does not necessarily have a causal relationship with this treatment. An AE can therefore be any unfavorable and unintended sign (including an abnormal laboratory finding), symptom, or disease temporally associated with the use of a medicinal (investigational) product, whether or not related to the medicinal (investigational) product.

Events Meeting the AE Definition

Any abnormal laboratory test results (hematology, clinical chemistry, or urinalysis) or other safety assessments (eg, ECG, radiological scans, vital signs measurements), including those that worsen from baseline, that are considered clinically significant in the medical and scientific judgment of the investigator (ie, not related to progression of underlying disease)Exacerbation of a chronic or intermittent pre-existing condition including either an increase in frequency and/or intensity of the conditionNew conditions detected or diagnosed after study intervention administration even though it may have been present before the start of the studySigns, symptoms, or the clinical sequelae of a suspected intervention-intervention interactionSigns, symptoms, or the clinical sequelae of a suspected overdose of either study drug or a concomitant medication. Overdose per se will not be reported as an AE/SAE unless it is an intentional overdose taken with possible suicidal/self-harming intent; such overdoses should be reported regardless of sequelae.
Events NOT Meeting the AE Definition

Any clinically significant abnormal laboratory findings or other abnormal safety assessments that are associated with the underlying disease, unless judged by the investigator to be more severe than expected for the participant's conditionThe disease/disorder being studied or expected progression, signs, or symptoms of the disease/disorder being studied, unless more severe than expected for the participant's conditionMedical or surgical procedure (eg, endoscopy, appendectomy): the condition that leads to the procedure is the AESituations in which an untoward medical occurrence did not occur (social and/or convenience admission to a hospital)Anticipated day-to-day fluctuations of pre-existing disease(s) or condition(s) present or detected at the start of the study that do not worsen

Serious Adverse Event (SAE)

An SAE is an AE occurring during any study phase (ie, at baseline or during Treatment, washout, or Follow-up), and at any dose of study drug that fulfills 1 or more of the following:

- Results in death
- Is immediately life-threatening (The term “life-threatening” refers to an event in which the participant was at risk of death at the time of the event. It does not refer to an event that hypothetically might have caused death if it were more severe.)
- Requires inpatient hospitalization or prolongation of existing hospitalization
- Results in persistent or significant disability or incapacity: a substantial disruption of a person’s ability to conduct normal life functions
- Results in a congenital abnormality or birth defect
- Is an important medical event that may require medical intervention to prevent 1 of the outcomes listed above.

Adverse Events of Special Interest (AESIs)

Based on the mechanism of action of sGC and anticipated vasodilation effects and based on the fact that CY6463 is a CNS-penetrant stimulator of sGC, the sponsor will collect AESIs in a timely manner. The AESIs relate to symptomatic hypotensive events and/or tachycardia, dizziness, syncope, and TEAEs related to change of neurobehaviors (ie, suicidality or euphoria).

In addition, because the marketed sGC stimulator riociguat includes bleeding events as a warning and precaution on its prescribing information (14), bleeding events will also be considered AESIs for CY6463 in this study. The specific list of AESI terms will be provided in the safety management plan.

An AESI classification means that although an event might be nonserious, it will nonetheless be reported to the sponsor by completing the AE eCRF and filling in the AESI box within 5 business days of the investigator’s first awareness of the AESI event.

Treatment-Emergent Adverse Event (TEAE)

A TEAE is defined as an AE that started on or after the administration of randomized study drug through the last day of the Follow-up period.

Recording of AEs and/or SAEs

When an AE/SAE occurs, it is the responsibility of the investigator to review all documentation (eg, hospital progress notes, laboratory reports, and diagnostics reports) related to the event. The investigator will then record all relevant information in the AE eCRF page.

- It is **not** acceptable for the investigator to send photocopies of the participant’s medical records in lieu of completion of the AE eCRF.
- There may be instances when copies of medical records for certain cases are requested by the Safety CRO. In this case, all participant identifiers, with the

exception of the participant number, will be redacted on the copies of the medical records before submission to the Safety CRO.

AE terms should be reported in standard medical terminology when possible. For each AE, the investigator will evaluate the event based on signs, symptoms, and/or other clinical information. Whenever possible, the diagnosis (not the individual signs/symptoms) will be documented as the AE/SAE. The investigator will complete the AE CRF in its entirety, including details regarding event onset (date and time), resolution (date and time), intensity, causality, action taken, serious outcome (if applicable), whether or not any medications were given in response to the event and whether or not the event caused the participant to discontinue the study.

Assessment of Intensity

Intensity will be assessed by the investigator according to the following scale:

- **Mild:** An event that is easily tolerated by the participant, causing minimal discomfort and not interfering with everyday activities
- **Moderate:** An event that causes discomfort sufficient to interfere with normal everyday activities
- **Severe:** An event that prevents normal everyday activities

It is important to distinguish between serious and severe AEs. Severity is a measure of intensity whereas seriousness is defined by the criteria of this Appendix. An AE of severe intensity may or may not be considered serious.

Relationship to Study Drug

For all AEs, the investigator must provide an assessment of causal relationship to study drug. The causality assessment will be recorded in the participant's source documentation and on the AE eCRF. The investigator may change his/her opinion of causality in light of follow-up information and amend the eCRF with the updated causality assessment.

Causal relationship will be assessed according to the criteria below.

Related:	An event where there is at least a reasonable possibility of a causal relationship between the event and the study drug. "Reasonable possibility" means there is evidence to suggest a potential causal relationship between the drug and the event.
Unrelated:	Any other event

[figure not shown]
